7. ACTIONS REQUIRED FOR REPEAT EPISODES OF POTENTIAL HY'S LAW

This section is applicable when a patient meets PHL criteria on study treatment (including the 30-day follow-up period) and has already met PHL criteria at a previous on study treatment visit.

The requirement to conduct follow-up, review and assessment of a repeat occurrence(s) of PHL is based on the nature of the alternative cause identified for the previous occurrence.

The investigator should determine the cause for the previous occurrence of PHL criteria being met and answer the following question:

- Was the alternative cause for the previous occurrence of PHL criteria being met chronic or progressing malignant disease or did the patient meet PHL criteria prior to starting study treatment and at their first on study treatment visit as described in Section 6

If No: follow the process described in Section 4.2 of this Appendix

If Yes:

Determine if there has been a significant change in the patient's condition[#] compared with when PHL criteria were previously met

- If there is no significant change no action is required
- If there is a significant change follow the process described in Section 4.2 of this Appendix

[#] A 'significant' change in the patient's condition refers to a subsequent clinically relevant change in any of the individual liver biochemistry parameters (ALT, AST or TBL) in isolation or in combination, or a clinically relevant change in associated symptoms, such as fatigue, vomiting, rash, right upper quadrant pain, jaundice, eosinophilia. The determination of whether there has been a significant change will be at the discretion of the Investigator; this may be in consultation with the Study Physician if there is any uncertainty.

1. INTRODUCTION

This appendix details the implementation of Response Evaluation Criteria In Solid Tumours (RECIST) 1.1 guidelines ([Eisenhauer et al 2009](#)) for the D4191C00003 study with regards to Investigator assessment of tumour burden including protocol-specific requirements for this study.

2. DEFINITION OF MEASURABLE, NON-MEASURABLE, TARGET AND NON-TARGET LESIONS

Only patients with measurable disease at baseline should be included in the study. Measurable disease is defined by the presence of at least one measurable lesion which has not been previously irradiated.

Tumour lesions selected for screening biopsy must not be used as index lesions.

Measurable:

A lesion, not previously irradiated, that can be accurately measured at baseline as ≥ 10 mm in the longest diameter (except lymph nodes which must have short axis ≥ 15 mm) with computed tomography (CT) or magnetic resonance imaging (MRI) and which is suitable for accurate repeated measurements.

Non-measurable:

- All other lesions, including small lesions (longest diameter < 10 mm or pathological lymph nodes with ≥ 10 mm to < 15 mm short axis at baseline¹).
- Truly non-measurable lesions include the following: bone lesions, leptomeningeal disease, ascites, pleural/pericardial effusion, inflammatory breast disease, lymphangitic involvement of skin or lung, abdominal masses/abdominal organomegaly identified by physical examination that is not measurable by CT or MRI.
- Tumour lesions selected for screening biopsy.
- Previously irradiated lesions²
- Skin lesions assessed by clinical examination

¹ Nodes with < 10 mm short axis are considered non-pathological and should not be recorded or followed as non-target lesions (NTLs).

² Localised post-radiation changes which affect lesion sizes may occur. Therefore, lesions that have been previously irradiated will not be considered measurable and must be selected as NTL at baseline and followed up as part of the NTL assessment.

- Brain metastasis

Special cases:

- Lytic bone lesions or mixed lytic–blastic lesions, with identifiable soft tissue components, can be considered measurable if the soft tissue component meets the definition of measurability. Blastic lesions are considered non-measurable.
- Cystic metastases can be considered measurable lesions if they meet the criteria for measurability from a radiological point of view, but if non-cystic lesions are present in the same patient, these should be selected as target lesions (TLs).

Target lesions:

A maximum of 5 measurable lesions (with a maximum of 2 lesions per organ), representative of all lesions involved suitable for accurate repeated measurement, should be identified as TLs at baseline.

Non-target lesions:

All other lesions (or sites of disease) not recorded as TL should be identified as NTL at baseline.

3. METHODS OF ASSESSMENT

The same method of assessment and the same technique should be used to characterize each identified and recorded lesion at baseline and during follow-up visits.

A summary of the methods to be used for RECIST assessment is provided in Table 1 and those excluded from tumour assessments for this study are highlighted, with the rationale provided.

Table 1 Summary of methods of assessment

Target lesions	Non-target lesions	New lesions
CT (preferred)	CT (preferred)	CT (preferred)
MRI	MRI	MRI
	Clinical examination	Clinical examination
	X-ray, Chest X-ray	X-ray, Chest X-ray
		Ultrasound
		Bone scan
		FDG-PET

CT Computed tomography; FDG-PET 18-Fluoro-deoxyglucose positron emission tomography; MRI Magnetic resonance imaging.

3.1 CT and MRI

CT and MRI are generally considered to be the best currently available and reproducible methods to measure TL selected for response assessment and to assess NTL and identification of any new lesions.

In the D4191C00003 study it is recommended that CT examinations of the chest and abdomen, (including liver and adrenal glands) will be used to assess tumour burden at baseline and follow-up visits. CT examination with intravenous contrast media administration is the preferred method. MRI should be used where CT is not feasible or it is medically contra-indicated. For brain lesion assessment, MRI is the preferred method.

3.2 Clinical examination

In the D4191C00003 study, clinical examination will not be used for assessment of TL. Clinically detected lesions can be selected as TLs if they are assessed by CT or MRI scans. Clinical examination can be used to assess NTL and to identify the presence of new lesions.

3.3 X-ray

3.3.1 Chest X-ray

In the D4191C00003 study, chest X-ray assessment will not be used for assessment of TL as they will be assessed by CT examination or MRI examination. Chest X-ray can, however, be used to assess NTL and to identify the presence of new lesions.

3.3.2 Plain X-ray

In the D4191C00003 study plain X-ray may be used as a method of assessment for bone NTL and to identify the presence of new bone lesions.

3.4 Ultrasound

In the D4191C00003 study, ultrasound examination will not be used for assessment of TL and NTL as it is not a reproducible method, does not provide an accurate assessment of tumour size and it is subjective and operator dependent. Ultrasound examination can, however, be used to identify the presence of new lesions. If new clinical symptoms occur and an ultrasound is performed then new lesions should be confirmed by CT or MRI examination.

3.5 Endoscopy and laparoscopy

In the D4191C00003 study, endoscopy and laparoscopy will not be used for tumour assessments as they are not validated in the context of tumour assessment.

3.6 Tumour markers

In the D4191C00003 study tumour markers will not be used for tumour response assessments as per RECIST 1.1.

3.7 Cytology and histology

In the D4191C00003 study histology will not be used as part of the tumour response assessment as per RECIST 1.1.

Cytological confirmation of the neoplastic origin of any effusion that appears or worsens during treatment is required when the measurable tumour has met criteria for response or stable disease. In such circumstances, the cytology is necessary to differentiate between response/stable disease (an effusion may be a side effect of the treatment) and progressive disease (if the neoplastic origin of the fluid is confirmed). Where cytology findings are not available, any effusion that significantly worsens (from trace to large) or appearance of clinically significant effusion (requiring change in drug therapy) during the study treatment will be considered to be progression of NTL, or disease progression due to new lesions.

3.8 Isotopic bone scan

Bone lesions identified on an isotopic bone scan at baseline and confirmed by CT, MRI or X-ray at baseline should be recorded as NTL and followed by the same method as per baseline assessment.

In the D4191C00003 study isotopic bone scans may be used as a method of assessment to identify the presence of new bone lesions at follow-up visits. New lesions will be recorded where a positive hot-spot that was not present on the baseline bone scan assessment is identified on a bone scan performed at any time during the study. The Investigator should consider the positive hot-spot to be a significant new site of malignant disease and represent true disease progression in order to record the new lesion. Confirmation by CT, MRI and X-ray is recommended where bone scan findings are equivocal.

3.9 FDG-PET scan

In the D4191C00003 study, 18-Fluoro-deoxyglucose positron emission tomography (FDG-PET) scans may be used as a method for identifying new lesions, according with the following algorithm: New lesions will be recorded where there is positive 18-Fluoro-deoxyglucose uptake³ not present on baseline FDG-PET scan or in a location corresponding to a new lesion on CT/MRI at the same follow-up visit. If there is no baseline FDG-PET scan available, and no evidence of new lesions on CT/MRI scans then follow-up CT/MRI assessments should be continued, scheduled as per protocol or clinical indicated, in order to confirm new lesions.

³ A positive FDG-PET scan lesion should be reported only when an uptake greater than twice that of the surrounding tissue is observed.

4. TUMOUR RESPONSE EVALUATION

4.1 Schedule of evaluation

The methods of assessment of tumour burden used at baseline CT/MRI scans of the chest and abdomen (including liver and adrenal glands) must be used at each subsequent follow-up assessment. Additional imaging may be performed based on the signs and symptoms of the patient e.g new lesions at follow-up.

The baseline assessment should be performed no more than 28 days before the start of MEDI4736 treatment and ideally as close as possible to the start of investigational product. Efficacy for all patients will be assessed by objective tumour assessments every 8 weeks for the first 48 weeks (relative to the date of the first MEDI4736 infusion; see [Table 1](#) of the Clinical Study Protocol), then every 12 weeks after discontinuation of MEDI4736 in patients who have disease control after 12 months of treatment ([Table 2](#) of the Clinical Study Protocol) until confirmed objective disease progression as defined by RECIST 1.1 (irrespective of the reason for stopping treatment/or subsequent therapy). If an unscheduled assessment is performed, and the patient has not progressed, every attempt should be made to perform the subsequent assessments at their scheduled visits.

For patients who discontinue MEDI4736 due to toxicity in the absence of confirmed objective progression objective tumour assessments should be continued every 8 weeks for 48 weeks (relative to the date of the first MEDI4736 infusion) then every 12 weeks until confirmed objective disease progression.

Disease progression requires confirmation, the confirmatory scan should occur preferably at the next scheduled visit and no earlier than 4 weeks after the initial assessment of PD in the absence of clinically significant deterioration.

If progression is not confirmed then the patient should continue on study treatment and on treatment assessments.

If an unscheduled assessment was performed and the patient has not progressed, every attempt should be made to perform the subsequent assessments at their scheduled visits. This schedule is to be followed in order to minimise any unintentional bias caused by some patients being assessed at a different frequency than other patients.

Additional assessments will be performed post-confirmed objective disease progression for patients remaining on study treatment, re-treatment or until subsequent cancer therapy according to the clinical study protocol.

4.2 Target lesions

4.2.1 Documentation of target lesions

A maximum of 5 measurable lesions, with a maximum of 2 lesions per organ (including lymph nodes), representative of all lesions involved should be identified as TL at baseline.

Target lesions should be selected on the basis of their size (longest diameter for non-nodal lesions or short axis for nodal lesions), but in addition should be those that lend themselves to reproducible repeated measurements. It may be the case that, on occasion, the largest lesion does not lend itself to reproducible measurement in which circumstance the next largest lesion, which can be measured reproducibly, should be selected.

The site and location of each TL should be documented as well as the longest diameter for non-nodal lesions (or short axis for lymph nodes). All measurements should be recorded in millimetres. At baseline the sum of the diameters for all TL will be calculated and reported as the baseline sum of diameters. At follow-up visits the sum of diameters for all TL will be calculated and reported as the follow-up sum of diameters.

Special cases:

- For TL measurable in 2 or 3 dimensions, always report the longest diameter. For pathological lymph nodes measurable in 2 or 3 dimensions, always report the short axis.
- If the CT/MRI slice thickness used is >5 mm, the minimum size of measurable disease at baseline should be twice the slice thickness of the baseline scan.
- If a lesion has completely disappeared, the longest diameter should be recorded as 0 mm.
- If a TL splits into two or more parts, then record the sum of the diameters of those parts.
- If two or more TLs merge then the sum of the diameters of the combined lesion should be recorded for one of the lesions and 0 mm recorded for the other lesion(s).
- If a TL is believed to be present and is faintly seen but too small to measure, a default value of 5 mm should be assigned. If an accurate measure can be given, this should be recorded, even if it is below 5 mm.
- If a TL cannot be measured accurately due to it being too large, provide an estimate of the size of the lesion.
- When a TL has had any intervention eg, radiotherapy, embolisation, surgery, during the study, the size of the TL should still be provided where possible.

4.2.2 Evaluation of target lesions

This section provides the definitions of the criteria used to determine objective tumour visit response for TL (see [Table 2](#)).

Table 2 Evaluation of target lesions

Complete Response (CR)	Disappearance of all TLs since baseline. Any pathological lymph nodes selected as TLs must have a reduction in short axis to <10 mm.
Partial Response (PR)	At least a 30% decrease in the sum of the diameters of TL, taking as reference the baseline sum of diameters
Stable Disease (SD)	Neither sufficient shrinkage to qualify for PR nor sufficient increase to qualify for PD
Progression of disease (PD)	At least a 20% increase in the sum of diameters of TLs, taking as reference the smallest sum on study (this includes the baseline sum if that is the smallest on study). In addition to the relative increase of 20%, the sum must also demonstrate an absolute increase of at least 5 mm.
Not Evaluable (NE)	Only relevant if any of the TLs were not assessed or not evaluable or had a lesion intervention at this visit. Note: if the sum of diameters meets the progressive disease criteria, progressive disease overrides not evaluable as a TL response

CR Complete response; PR Partial response; PD Progression of disease; NE Not evaluable; SD Stable disease; TL Target lesion.

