5.6 Concomitant and post-study treatment(s)

Investigators may prescribe concomitant medications or treatments (eg, acetaminophen, diphenhydramine) deemed necessary to provide adequate prophylactic or supportive care except for those medications identified as "excluded" as listed below:

- Any investigational anti-cancer therapy
- Any concurrent chemotherapy, radiotherapy, immunotherapy, biologic, or hormonal therapy for cancer treatment. Concurrent use of hormones for non cancer-related conditions (eg, insulin for diabetes and hormone replacement therapy) is acceptable. Note: Local treatment of isolated lesions, excluding target lesions, for palliative intent is acceptable (eg, by local surgery or radiotherapy).
- Immunosuppressive medications including, but not limited to systemic corticosteroids at doses beyond 10 mg/day of prednisone or equivalent, methotrexate, azathioprine, and tumour necrosis factor alpha blockers. Use of immunosuppressive medications in patients for the management of investigational product-related AEs or their use in patients with contrast allergies is acceptable. In addition, use of inhaled and intranasal corticosteroids is permitted.
- Live attenuated vaccines within 30 days of MEDI4736 dosing. Inactivated viruses such as those in the influenza vaccine are permitted.

Other medication, which is considered necessary for the patient's safety and well being, may be given at the discretion of the investigator and recorded in the appropriate sections of the eCRF.

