11.1 Calculation or derivation of efficacy variable(s)

11.1.1 RECIST 1.1 based endpoints

11.1.1.1 Independent Central Review of RECIST 1.1-based assessments

The ICR of all radiological imaging data will be carried out using RECIST version 1.1. All radiological scans for all patients (including those at unscheduled visits, or outside visit windows) will be provided to the ICR. Prior radiotherapy reports will also be provided to the ICR to allow the selection of appropriate target lesions. The imaging scans will be reviewed by 2 independent radiologists using RECIST 1.1 and will be adjudicated, if required. For each patient, the ICR will define the overall visit response data (CR, PR, SD, PD or not evaluable) and the relevant scan dates for each time point (ie, for visits where response or progression is/is not identified). If a patient has had a tumour assessment that cannot be evaluated then the patient will be assigned a visit response of not evaluable (unless there is evidence of progression in which case the response will be assigned as PD). All RECIST endpoints will be derived from the overall visit response date and the scan dates.

Further details of the ICR will be documented in the ICR Charter.

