12.2.1 Objective response rate

The primary endpoint, ORR, will be estimated for each cohort with 95% exact CIs. The primary analysis will be based on the programmatically derived ORR based on ICR assessments, and using all scans regardless of whether they were scheduled or not. An analysis of ORR using the results of the programmatically derived RECIST using the site investigator tumour data from all scans will be conducted as a sensitivity analysis to confirm the results of the primary analysis using data derived from the eCRFs. An additional sensitivity analysis will be performed on programmatically derived ORR using ICR data (RECIST modified for confirmation of progression) to determine if there is any difference when using progression confirmation rules. The primary analysis population for ORR will be a subset of the FAS population (ie, dosed patients with a baseline tumour assessment that indicates measurable disease per the ICR).

Summaries will be produced that present the number and percentage of patients with a tumour response (CR/PR). The number (%) of patients with a confirmed response and the number (%) of patients with a single visit response (ie, an unconfirmed response) will also be presented.

Summaries of ORR for each cohort will also be presented for the irRECIST 1.1 data obtained from the ICR.

A supportive analysis of patients with unselected PD-L1 status will be conducted consisting of a combined population of PD-L1 positive and PD-L1 negative/unknown patients, including those also enrolled after the protocol amendment to only recruit patients with PD-L1 positive status (ie, all Cohort 2 patients). This will use a weighted approach based on the observed

prevalence of PD-L1 positive, PD-L1 negative and PD-L1 unknown patients from the unselected sample pre-amendment. Further details of this approach will be provided in the SAP.

Furthermore, summaries of ORR (using the programmatically derived ORR based on ICR assessments) may also be presented by cohort for the PD-L1 negative patients in Cohort 1, and additionally, for all patients in a combined population of Cohorts 1 and 2.

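### Appendix F makes a locally treated target lesion not evaluable only at the visit concerned, so its later shrinkage can be scored as response, directly in the investigator-assessed ORR and possibly in the primary ICR ORR

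*Protocol*

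**What the plan says.** Appendix F, Section 4.2.2, Table 2 gives this condition for a not-evaluable (NE) target-lesion response: "Only relevant if any of the TLs were not assessed or not evaluable or had a lesion intervention at this visit". A note adds that PD overrides NE if the sum meets the PD criteria.

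Appendix F, Section 4.2.1 foresees on-study treatment of target lesions (TLs): "When a TL has had any intervention eg, radiotherapy, embolisation, surgery, during the study, the size of the TL should still be provided where possible". On the sum it says: "At follow-up visits the sum of diameters for all TL will be calculated and reported as the follow-up sum of diameters". A lesion that has disappeared is entered as 0 mm. Target PR is defined as: "At least a 30% decrease in the sum of the diameters of TL, taking as reference the baseline sum of diameters".

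Appendix F describes its scope as "Investigator assessment of tumour burden including protocol-specific requirements for this study", and Section 11.1.1.2 assigns investigator visit responses by program from its definitions. For the main endpoint, Section 12.2.1 states: "The primary analysis will be based on the programmatically derived ORR based on ICR assessments". On what the central readers receive, Section 11.1.1.1 states: "Prior radiotherapy reports will also be provided to the ICR to allow the selection of appropriate target lesions". It leaves further detail to the ICR Charter.

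Section 5.6 accepts palliative local treatment of isolated lesions but excludes target lesions. Section 5.1 allows palliative radiotherapy to bone metastases present at baseline and leaves other sites to case-by-case discussion.

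**The concern.** In a single-arm study, ORR measures drug activity only if the credited shrinkage comes from the drug. Appendix F, Section 2 accepts this at baseline: previously irradiated lesions are not measurable, because radiation changes can affect their size. Table 2 does not carry that reasoning forward to lesions treated during the study. Its NE condition is tied to the current visit, and nothing removes the lesion from later sums.

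No other rule clearly closes the gap. Section 11.1.3 disallows responses after subsequent therapy only for patients who have discontinued treatment, so a local procedure while on drug is not covered. Confirmation offers no protection either, because a resected or successfully irradiated lesion stays small at the confirming scan.

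At stake is a response credited to the drug that belongs to a local procedure, with no control arm to show the error.

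**Working it through.** **1. The plan's own figures.** Clopper-Pearson 95% intervals for the Section 12.3 examples:
- 20/80 = 25.0%: 15.99% to 35.94% (protocol: 16.0% to 35.9%)
- 32/80 = 40.0%: 29.20% to 51.56% (protocol: 29.2% to 51.6%)

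Both reproduce.

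**2. When a treated lesion alone gives target PR.** Let *s* be the treated lesion's share of the baseline sum and *f* its fractional shrinkage, with the other TLs unchanged. The sum falls by *s × f*, so PR needs *s × f* ≥ 0.30. For a lesion recorded as 0 mm, *f* = 1 and the condition is *s* ≥ 0.30.

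| Baseline TLs (mm), first one removed | Sum before → after | Change | Target response |
|---|---|---|---|
| 30 + 50 | 80 → 50 | −37.5% | PR |
| 40 + 40 + 40 | 120 → 80 | −33.3% | PR |
| 20 + 80 | 100 → 80 | −20.0% | SD |

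**3. A worked sequence (invented sizes).** TLs of 40 + 20 = 60 mm; the 40 mm lesion is irradiated between Weeks 8 and 16.
- Week 16: NE, if the first scan after the procedure is taken as the visit of the intervention.
- Week 24: 20 + 20 = 40 mm; (40 − 60)/60 = −33.3%.
- Week 32: 18 + 20 = 38 mm; (38 − 60)/60 = −36.7%.

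Weeks 24 and 32 are 8 weeks apart, beyond the 4-week minimum. This is a confirmed PR, given no non-target progression and no new lesion, although the untreated lesion never changed.

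**4. A single TL, resected.** If it is entered as 0 mm, Appendix F Table 4 gives overall CR only when non-target lesions are absent at baseline or also CR and there is no new lesion. With persisting, non-progressing non-target disease the result is PR. Either counts towards ORR.

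**5. Can it occur?** Section 5.6 makes it uncommon but does not exclude it. The Section 5.1 provision for baseline bone metastases has no target-lesion exception, and Appendix F, Section 2 lets lytic or mixed bone lesions with a measurable soft-tissue part count as measurable. Section 4.2.1 itself anticipates treated TLs.

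**6. Route to the primary endpoint.** The ICR assesses independently, and Section 6.3.2 says its results are not sent to investigators. Section 12.3 already expects about 15% of patients measurable per site not to be measurable per ICR. A site can therefore treat what it regards as a non-target lesion while the ICR follows it as a target.

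**7. Size.** With about 80 patients in the ICR denominator, one patient is 1/80 = 1.25 points. The investigator-based denominator is about 94, so there it is 1/94 = 1.06 points. The documents give no count of affected patients; the range below is an assumption. Starting from 20/80 and removing responders who owe their response to a treated lesion:

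| Removed | ORR | Exact 95% CI |
|---|---|---|
| 1 | 19/80 = 23.75% | 14.95% to 34.58% |
| 2 | 18/80 = 22.50% | 13.91% to 33.21% |
| 4 | 16/80 = 20.00% | 11.89% to 30.44% |

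**The case against.** **The wording can be read more kindly.** The NE condition might mean that a lesion bearing a past intervention is being assessed at this visit; it would then remain NE. That reading is possible and may be what was intended. It is not what the words most naturally say. On the strictest reading, a procedure between two scans happens at no visit, so even Week 16 in the sequence above would not be NE. A program needs one reading.

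**Recording the size has a proper use.** The PD override needs measurements of treated lesions. This stands: the instruction to measure is sound, and the defect is only that response may also be credited.

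**Table 2 does not govern the primary endpoint.** A reader might infer that the rule itself inflates the primary ORR. The documents do not support that. Appendix F covers investigator assessment, and the ICR sets its own visit responses under a Charter that is not shown.

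**The ICR is not said to receive prior radiotherapy reports alone.** A reader might infer this from Section 11.1.1.1. The sentence concerns the choice of baseline targets; on-study records are neither mentioned nor excluded.

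**Exposure is narrow.** Section 5.6 excludes TLs from permitted local treatment, most bone lesions are not measurable, and Section 5.8 requires discontinuation when alternative anti-cancer therapy starts. This limits the frequency but does not repair the rule.

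**The shift is small against the interval.** True: 1.25 points against a width of about 20 points, with no hypothesis test planned. The error in ORR does, however, run only towards more responses.

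**Conclusion.** The point holds as a defect in a written rule. On a literal reading, Appendix F lets shrinkage of a target lesion treated on study count as PR or CR from a later scan, and such a response would be confirmed. The direct effect is on the investigator-assessed ORR. For the primary ICR ORR there is a possible route, conditional on differing target selection and on the Charter not supplying on-study treatment records.

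The size is 1.25 points of a cohort's ICR ORR per affected patient, assuming 80 evaluable. The number of patients is unknown and should be low.

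Two further inferences should not be drawn. A resected single target lesion does not always give an overall CR; persisting non-target disease makes it PR. Nor do DoR, DCR and PFS simply carry the same bias: a treated lesion also lowers the nadir against which PD is judged, so PFS can move in either direction.

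**What to change.** In Appendix F Table 2, replace the restriction to the current visit with wording to this effect: once a TL has had an intervention during the study, it is handled as a treated lesion at that and every later visit; CR or PR may not be credited from its shrinkage; PD still overrides; and the scans count as performed assessments for PFS and DoR censoring and for the missed-visit rule.

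The last clause is needed. A blanket NE at all later visits would, under Section 11.1.7, move censoring back to the last evaluable scan and might trigger the rule on two or more missed visits, although the patient was scanned. DoR takes its censoring from PFS.

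In Section 11.1.1.1, state that dates and sites of on-study radiotherapy, embolisation and surgery are given to the ICR, or applied in the programmed derivation, under the same rule. If the Charter already says so, a cross-reference is enough.

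The cost is two short text changes and a data transfer; palliative radiotherapy is already an item in the study schedules. The downside is that a few genuine responses in locally treated patients would not be credited.
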